### **13.4 Reports**

Publications and annual reports for submission to the IRB and FDA will be written by the [REDACTED] using the data captured on the eCRFs.

### **14. Data and Safety Monitoring**

Monitoring of this study will occur in accordance with the [REDACTED] approved Data and Safety Monitoring Plan (DSMP). An "initiation audit" will be conducted at [REDACTED] in accordance with the DSMP following enrollment of the first two (2) or three (3) patients. Subsequent audits will occur on an annual basis prior to annual IRB continuing review, if the findings from the initiation audit were satisfactory. More frequent audits of patient data and study conduct will occur if necessary. Prior audit findings and/or situations that may arise during the course of the study will determine the need for more frequent auditing. All audit findings will be discussed with the principal investigator and reported to the [REDACTED]

## **15. Multi-Institutional Guidelines**

### **15.1 IRB Approvals**

As the Coordinating Center for a trial, it is the [REDACTED] responsibility to ensure that no patients are entered on the trial at a participating institution without full IRB approval. Thus, OHRS will approve the addition of each participating institution to the study. A copy of the IRB approval document from each participating institution will be obtained by the OHRS prior to activation of the study at the participating institution.

### **15.2 Other Pre-Study Documents**

Each participating center is required to have the following documents on file at OHRS:

- Curricula Vitae of all physician Investigators
- Signed FDA form 1572 of all physician Investigators (if applicable)
- [REDACTED] of all physician Investigators
- Documentation of Human Subjects Protection training from all Investigators
- Signed Investigator agreement from the Principal Investigator at each participating center
- Medical license from each Investigator

### **15.3 Initiation Meetings**

A study initiation meeting will be conducted with each participating institution prior to enrollment of patients from the institution. OHRS staff will conduct the study initiation meeting in close proximity to IRB approval of the study at the participating center. In most situations the study initiation meeting will be conducted via teleconference. Web-based training regarding e-CRF completion will be utilized as appropriate.

### **15.4 IRB Continuing Approvals**

Investigators from participating institutions must provide the [REDACTED], through OHRS, a copy of the institution's approved continuing review documentation. Registration will be halted

Protocol Version 8.0 12/01/2017

CINJ #: 081501

Title: A Phase 2 Randomized Discontinuation Trial in Patients with Hormone-Dependent Rising Prostate-Specific Antigen Progression After Local Therapy for Prostate Cancer Evaluating the Synergy of Metformin Plus Aspirin (PRIMA Trial).

PI: [REDACTED]

at any participating institution in which a current continuing approval is not on file at OHRS. Centers that are approved to utilize the Rutgers University central IRB will not be required to file continuing review documentation.

#### **15.5 Amendments and Consents**

OHRS will maintain a copy of all amendments, consent forms and approvals from each participating institution. Consent forms will be reviewed and approved by OHRS to ensure consistency with the IRB approved consent. Should changes to the protocol become necessary, protocol amendments will be submitted in writing to the [REDACTED] and local IRB for approval prior to implementation; unless the patient's best interest is endangered. In that case, notification to [REDACTED] and local IRB will be made as soon as possible.

#### **15.6 Patient Registration**

All patients from participating institutions must register patients with the OHRS central Registration Desk, as described in Section 5.7 of this protocol.

#### **15.7 Data Collection and Toxicity Reporting**

The PI at each institution will be responsible for assuring that all the required data is collected and entered onto the eCRFs accurately and completed eCRFs submitted as described in Section 13.

#### **15.8 Data Monitoring and Source Document Verification**

[REDACTED] staff will conduct monitoring visits to participating institutions of [REDACTED] Oncology Group no less frequently than every 3 months. The monitoring visits will focus on verifying eCRF data with source documents. Adherence to the protocol(s), including the prompt reporting of serious adverse events, will be assessed. Findings of all monitoring visits are recorded in a [REDACTED] Monitors Report, which is kept on file in the OHRS regulatory file. Issues concerning study compliance are at regular meetings of the [REDACTED] Human Research Oversight Committee.

#### **15.9 Data and Center Audits**

[REDACTED] staff will conduct annual audits to participating centers in accordance with OHRS Standard Operating Procedures (SOPs). The audit guidelines are in accordance with the [REDACTED] and Safety Monitoring Plan.

### **16. Statistical Considerations**

#### **16.1 Primary Hypothesis**

The primary hypothesis is that metformin and aspirin will result in persistent stable disease in patients randomized to receive these medications after a run in period. By comparison patients with stable disease after a four-month run in period, who are randomized to placebo will experience a greater rate of disease progression

Title: A Phase 2 Randomized Discontinuation Trial in Patients with Hormone-Dependent Rising Prostate-Specific Antigen Progression After Local Therapy for Prostate Cancer Evaluating the Synergy of Metformin Plus Aspirin (PRIMA Trial).

PI: [REDACTED]

## **16.2 Outcome Measures**

Difference in the stable PSA rates after 6 cycles of metformin and aspirin or placebo therapy will be calculated in patients who have received 4 cycles of open label treatment during the “run in phase”

## **16.3 Sample Size and Statistical Analysis**

In this study, we hypothesize that patients with stable PSA after 4 cycles of open label treatment who are then treated with 6 cycles of metformin and aspirin will have a 40% rate of PSA or clinical progression compared to 80% rate of progression in patients treated with placebo. With 28 patients randomized to treatment or placebo the study will have 80% power to detect an increase in the proportion of patients with progression at 6 cycles from 40% to 80% with alpha =0.05. Assuming that approximately 10 patients progress prior to randomization, a total of 66 patients will be entered on this study.

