**TOTAL NUMBER OF REGISTERED PATIENTS= 66 (assuming 10 patients progress prior to randomization)**

**TOTAL NUMBER OF RANDOMIZED PATIENTS= 56  

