28 PATIENTS PER ARM**

**STATISTICAL ANALYSIS:** With 28 patients randomized to treatment or placebo the study will have 80% power to detect an increase in the proportion of patients with progression at 6cycles from 40% to 80% with alpha =0.05

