In patients with rising PSA, drugs causing disease stabilization would be expected to lead to a slowing in the rate of rise in the PSA, which can also be expressed as a lengthening of the PSA doubling time. Multiple prior phase II trials for men with rising PSA, including several randomized placebo controlled trials, have assessed changes in PSA doubling time as an endpoint. In these trials it was noted that patients in the placebo arm often have an increase in the PSADT after going on study. As noted by Paller et al., in a Rosiglitazone trial involving 106 patients, 73% of patients on placebo had an increase of PSADT in excess of 100%, and 31% exceeded 200% in PSADT lengthening. In an Atrasentan trial involving 222 patients, 78% of the patients on placebo had a lengthening of PSADT. In a celecoxib trial involving 78 patients, 20% of the patients on placebo had >200% increase of PSADT. In these studies, the increase in pre and on-treatment PSA doubling time has been attributed to difference between spacing interval and number of PSA values collected in an uncontrolled “pre-study period compared to the regular intervals at which PSA values are collected once on study”.

In the current design all subjects will receive study therapy for 4 cycles. During this period PSA will be measured at monthly intervals in order to determine a PSA doubling time in a uniform manner, and to obtain a relatively homogeneous population of patients for randomization. Patients

Protocol Version 8.0 12/01/2017

Title: A Phase 2 Randomized Discontinuation Trial in Patients with Hormone-Dependent Rising Prostate-Specific Antigen Progression After Local Therapy for Prostate Cancer Evaluating the Synergy of Metformin Plus Aspirin (PRIMA Trial).

PI: [REDACTED]

meeting the study specified definition of stable disease will then proceed to randomization while patients meeting criteria for PSA progression will come off study and those patients with PSA response will continue on therapy until the study definition of disease progression is met.

After the run in phase patients meeting the criteria for stable disease will be randomized to continue therapy with metformin and aspirin or to placebo metformin, and placebo aspirin.

The secondary objective of this study is to determine whether the intervention may modify the PSA levels and the serum obesity-related PCa biomarkers. The tolerability of and compliance of metformin and aspirin treatment in these subjects will also be evaluated.

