#### **4.1 Disease Assessment After Run In Stage:**

After 4 cycles of treatment patients with disease progression (PSA increase of >50% and minimum of 2ng/ml rise in PSA) will come off study. Patients with disease response (>25% decline in PSA) will continue on study agents.

Patients with stable disease (not meeting criteria for progression or stable disease) will be randomized to continue on the study regimen or receive placebo therapy for 6 cycles.

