#### **4.4 PSA Responder Treatment:**

Patients meeting criteria for PSA response (>25% decline in PSA during the run-in phase) randomization will be assigned to continue therapy with metformin 500 mg in the morning and 1000 mg at night, and aspirin 81 mg per day until disease progression.

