## 7. Treatment Plan

### 7.1 General Considerations

Treatment will be administered on an outpatient basis. No investigational or commercial agents or therapies other than those described below may be administered with the intent to treat the patient's malignancy. Patients may discontinue therapy at any time for any reason.

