### 7.3 Dose Modifications or Escalations

#### 7.3.1 Toxicity

Any Grade 3 or 4 non-hematologic adverse event, or Grade  $\geq 2$  renal toxicity, thought to be drug-related will lead to cessation of medications. If any of these occur, the patient will be removed from the study.

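### The step from 66 registered to 56 randomised allows only for about 10 run-in progressors and nothing for PSA responders or other run-in exits, so 28 per arm, and possibly 80% power, is not secured

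*Combined protocol and SAP*

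**What the plan says.** **Numbers.** The Synopsis gives "TOTAL NUMBER OF REGISTERED PATIENTS= 66 (assuming 10 patients progress prior to randomization"), then 56 randomised, "28 PATIENTS PER ARM". Section 16.3 repeats this: "Assuming that approximately 10 patients progress prior to randomization, a total of 66 patients will be entered on this study". Both assume progression of 40% on metformin plus aspirin against 80% on placebo at 6 cycles, 80% power and alpha 0.05. Neither names the test or says whether it is one- or two-sided.

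**Who is randomised.** Only men with stable disease after the 4-cycle run-in. Progressors leave. Responders do not enter the comparison: Section 4.1 has "Patients with disease response (>25% decline in PSA) will continue on study agents", and the Clinical trial part of Section 2 has "those patients with PSA response will continue on therapy until the study definition of disease progression is met". Section 4.4 ("Patients meeting criteria for PSA response (>25% decline in PSA during the run-in phase") likewise assigns them to continued active treatment.

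**Other ways out during the run-in.** Section 7.1: "Patients may discontinue therapy at any time for any reason". Section 7.3.1, on specified drug-related toxicities: "If any of these occur, the patient will be removed from the study". Section 7.6.2 removes men who cannot keep compliance at 90%. Section 10 adds intercurrent illness, withdrawal and others.

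**PSA after stopping.** The Section 6 table has PSA every 4 weeks on treatment and at an off-treatment visit (+30 days). Footnote 7 puts everyone who stops early on PSA every 12–16 weeks, within a follow-up of 1 year from registration. Sections 4.6 and 7.7 also keep men who stop treatment in outcome follow-up.

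**The concern.** The design has three planned branches at the end of the run-in (progression, response, stable disease) plus unplanned exits, but the sample size provides for only one kind of loss. There is no expected number of responders or other exits, no replacement rule, and no rule that registration continues until 56 are randomised. If all run-in exits together exceed 10, fewer than 56 are randomised, and the plan states neither that number nor the power it would have.

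A separate weakness concerns men already randomised. The primary comparison is progression at 6 cycles, and PSA progression is one component of it. For a man who stops treatment early without having progressed, the sparser schedule may leave no PSA near the end of the window, so progression by then could be missed. If stopping differs between arms, ascertainment would be uneven. The removal wording in 7.3.1 and 7.6.2 adds to this if a site reads it as the end of data collection.

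**Working it through.** **1. Reproduce 28 per arm.** Inputs from 16.3: p1 = 0.40, p2 = 0.80, d = 0.40, alpha 0.05, power 80%. Taking a two-sided test (z = 1.960 and 0.842) and mean proportion 0.60:

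- Uncorrected: n0 = [1.960·√(2·0.6·0.4) + 0.842·√(0.4·0.6 + 0.8·0.2)]² / 0.4² = 22.33, so 23 per arm.
- Continuity-corrected: n = (n0/4)·[1 + √(1 + 4/(n0·d))]² = 27.10, so 28 per arm.

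The one-sided versions give 18 (uncorrected) and 23 (corrected). Of these four, only the two-sided continuity-corrected formula returns 28.

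**2. Reproduce 66.** 2 × 28 = 56 and 56 + 10 = 66. The sum is correct; the remainder for any other exit is 66 − 56 − 10 = 0. The break-even is 10/66 = 15.2% total run-in exits of all kinds.

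**3. Number randomised if there are other exits.** Assumption, since the documents give no rate: non-progression exits (responders plus all others) are 5–20% of 66, with progressors fixed at 10.

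| Other exits | Men lost | 56 minus lost | Per arm |
|---|---|---|---|
| 5% | 3.3 | 52.7 | 26 |
| 10% | 6.6 | 49.4 | 24 |
| 15% | 9.9 | 46.1 | 23 |
| 20% | 13.2 | 42.8 | 21 |

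In whole men, about 53 down to 42.

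**4. Power at 40% vs 80%, two-sided 0.05.** Uncorrected power = Φ{[0.4·√n − 1.960·√0.48]/√0.40}. The corrected version replaces n by n − 2/d + 1/(d²n); at 28 this is 28 − 5 + 0.22 = 23.22. Fisher's exact test is by full enumeration with equal arms.

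| n per arm | Continuity-corrected | Fisher | Uncorrected |
|---|---|---|---|
| 28 | 81.6% | 82.3% | 88.5% |
| 27 | 79.8% | 80.2% | 87.3% |
| 26 | 77.9% | 79.9% | 85.9% |
| 24 | 73.5% | 76.0% | 82.9% |
| 23 | 71.1% | 72.7% | 81.2% |
| 22 | 68.5% | 69.1% | 79.4% |
| 21 | 65.8% | 65.4% | 77.4% |

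Fisher power is not smooth in n: with 49 randomised as 25 and 24 it is 80.8–82.5%, depending on which arm is larger.

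**5. Registrations needed to keep 56.** On the same fixed-progressor basis, R·(1 − r) − 10 = 56, so R = 66/(1 − r). At 5%, 69.5, so 70; at 10%, 74; at 15%, 78; at 20%, 82.5, so 83.

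**6. PSA after an early stop.** Six 4-week cycles make a 24-week window. Assume the 12–16-week interval runs from the stop date (the anchor is not stated).

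| Stop at week | Next PSA, 12-weekly | Next PSA, 16-weekly | 4-weekly values forgone |
|---|---|---|---|
| 4 | 16 | 20 | 5 |
| 8 | 20 | 24 | 4 |
| 12 | 24 | 28 | 3 |
| 16 | 28 | 32 | 2 |
| 20 | 32 | 36 | 1 |

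A stop at week 12 yields a follow-up value by week 24 only at the shorter interval; stops at weeks 16 and 20 yield none. The off-treatment PSA comes on top: 30 days is about 4.3 weeks, so it falls no later than about week 20.3 for a week-16 stop and week 24.3 for a week-20 stop.

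**The case against.** **There is no arithmetic error.** A reader might infer one, but 66 − 10 = 56 = 2 × 28 is right. What is missing is a planning assumption. The 10 is approximate, and fewer progressors would offset other exits. The Synopsis also lists 56 randomised as a figure in its own right, so 66 can be read as an estimate of the registrations needed. That softens the point but does not remove it, because no text says registration continues until 56 are randomised.

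**Few responders may be expected.** Section 2 looks for slower PSA rise, not falls above 25%, and nothing in the documents suggests a material response rate. This is fair, and it is why the 5–20% range is only an assumption. It does not cover the non-response exits, and a low expectation can simply be written down.

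**Power may survive.** With an uncorrected test, 10 further losses (46 randomised, 23 per arm) still leave 81.2%; Fisher exceeds 80% at 49 randomised. The early fall is clearest under the continuity-corrected formula, which is inferred only because it returns 28. This stands: a reader might conclude that the trial will be underpowered, and the documents do not support that.

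**The PSA gap is partial.** Men who stop because of PSA progression (Section 10, item h) already have the endpoint. A week-20 stopper's off-treatment PSA can fall at the end of the window. If treatment starts near registration, the window ends at week 16 + 24 = 40, leaving 52 − 40 = 12 weeks of follow-up. Stops at window weeks 16 and 20 (study weeks 32 and 36) then have a PSA due at study weeks 44–48 and 48–52. A later value below threshold makes missed progression unlikely; one above it leaves open whether progression came before or after 6 cycles. So a reader who inferred that early stoppers have no usable PSA would go too far. What stands is that a value at the end of the window is not guaranteed.

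**The removal wording may mean removal from treatment only.** Section 10 has an off-study heading but text about continuing treatment, and 4.6 and footnote 7 expressly follow men who stop early. That is the likely intent, but 7.3.1 and 7.6.2 do not say so.

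**Conclusion.** The point holds as a gap in the planning assumptions. The 66 registrations deliver 28 per arm only if run-in exits of every kind total no more than 10, whereas the plan assigns all 10 to progression and its own design creates other exits. The size of any shortfall cannot be fixed from the documents. Under the assumed 5–20% non-progression exits with 10 progressors fixed, power at 26, 23 and 21 per arm is 77.9%, 71.1% and 65.8% (continuity-corrected) or 79.9%, 72.7% and 65.4% (Fisher), against 85.9%, 81.2% and 77.4% uncorrected. Loss of 80% power is therefore possible, not certain, and depends on unstated exit rates and an unnamed test.

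The PSA schedule is a separate and smaller matter that adds no weight to the sample-size point. For randomised men who stop without progression, especially around weeks 12–20, an end-of-window PSA is not assured, though the off-treatment and later follow-up values partly cover this. How many men are affected is unknown. Confidence is medium; the changes should be made.

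**What to change.** 1. **Section 16.3 and Synopsis.** State the assumed numbers of responders and other run-in exits beside the progressors, the expected number randomised, and the power at that number under a named two-sided test. If that power is below 80%, state the lower figure. Cost: a text amendment, with no extra patients.
2. **Only if the sponsor prefers to keep 56 randomised,** say so and plan for about 70–83 registrations (4–17 more than 66) at 5–20% non-progression exits, with progressors held at 10.
3. **Footnote 7.** For randomised men who stop treatment early without progression, add one PSA at the end of the 6-cycle window. Cost: one blood draw each.
4. **Wording.** Reconcile the removal language in 7.3.1 and 7.6.2 with the outcome follow-up in 4.6, footnote 7 and 7.7, so that it is clear whether data collection continues. This does not change when treatment stops.

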# **17. Human Subjects**

## **17.1 Subject Population**

Men with clinical stage D0 prostate cancer as evidenced by rising PSA values despite have received definite local therapy for prostate cancer (e.g., prostatectomy or radiation therapy)

## **17.2 Potential Risks**

Potential risks to the patient secondary to metformin include nausea, vomiting, diarrhea, and lactic acidosis. Potential risks for aspirin include peptic ulcer disease and GI bleeding. These will be monitored as detailed in Sections 6-8. In terms of the individual's prostate cancer, there is a risk of treatment not being effective. Furthermore, if the drug is not effective, there is the possibility of disease progression (either PSA rising further or by observable metastasis).

## **17.3 Consent Procedures**

Informed consent must be obtained prior to commencing any research procedures. The PI shall seek such consent only under such circumstances that provide the prospective patient opportunity to consider whether or not to participate and that minimize the possibility of coercion or undue influence. The information given to the patient, or the representative, shall be in a language understandable to the subject or representative. The informed consent document may not include any exculpatory language through which the subject or representative is made to waive any of the subject's legal rights or releases, or appears to release the investigator, the sponsor or the institution from liability for negligence.

## **17.4 Potential Benefits**

The benefits of participating in this study may be improvement in a patient's cancer either as a measure of disease activity or quality of life improvements.

## **17.5 Risk-Benefit Ratio**

All risks and benefits of this treatment will be discussed with the patient prior to enrollment on this study. Specifically, this includes that the patient's rising PSA value likely represents some

Protocol Version 8.0 12/01/2017

Title: A Phase 2 Randomized Discontinuation Trial in Patients with Hormone-Dependent Rising Prostate-Specific Antigen Progression After Local Therapy for Prostate Cancer Evaluating the Synergy of Metformin Plus Aspirin (PRIMA Trial).

PI: [REDACTED]

micrometastasis, and the possibility of further progression without some form of intervention. Along these lines, the basic principles of what we are hoping to accomplish with metformin and aspirin will be explained. The potential risks detailed in Section 17.2 will be made clear as well, along with what measures are in place to minimize these risks.

Alternative treatment will also be discussed. These options include beginning androgen ablation therapy, monitoring off therapy, or enrolling in another clinical trial. Additionally, the importance of the knowledge gained through this study will be discussed with the patient.

All told, with the combination of employing proper patient selection and study termination criteria, close clinical and lab follow-up (both of the prostate cancer as well as other relevant body systems), and with the medical knowledge of metformin and aspirin are being utilized in patient treatment (as an FDA-approved medication, for non-oncologic medical purposes). Therefore we believe that the potential benefits outweigh the risks of the trial.

